5.1.4 Visit 4 (Postoperative Day 7, ±2 days)

At Visit 4, the following assessments will be performed:

NOTE: All ocular assessments and VA will be performed bilaterally.

- AEs and changes in concomitant medications
- the unmasked designee must weigh both bottles of study drug
- ocular symptoms
- pediatric VA
- biomicroscopy
- IOP measurement

NOTE: Measurement of IOP must occur after the assessment of ocular symptoms, VA and biomicroscopy

- review study drug administration diary for compliance. Instruct subject's parent/legal guardian to record time of each instillation in the diary and to bring the diary and study drug (both bottles) to their next visit. Remind subject's parent/legal guardian that no other information should be recorded in the diary
- dispense new diary
- the unmasked designee must redispense study drug
- remind subject's parent/legal guardian that the dosing is QID for another week and then BID for one week

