The subject will receive the first dose of study drug by the unmasked designee at the end of the surgery. Either the unmasked designee or the subject's parent/legal guardian will then administer 1 to 2 drops of study drug to the lower cul-de-sac of the study eye once in the evening on the day of surgery and then four times a day (QID), at approximately four hour intervals, beginning on the morning after surgery. QID dosing will continue until postoperative day 14, including dosing at appropriate time intervals on the day of a visit. Treatment will be tapered from QID to twice a day (BID) during the interval between postoperative days 15 and 21. Treatment will be further tapered from postoperative day 22 until day 28 to once a day (QD) with the last dose being administered on the day prior to Visit 6 (Postoperative Day 28).

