4.3 Instructions for Use and Administration

Following the initial drop administration by the unmasked study personnel at the end of the surgery, either the unmasked designee or the subject's parent/legal guardian will administer 1 to 2 drops of study drug into the study eye once in the evening on the day of surgery and then QID, at approximately four hour intervals, beginning on the morning after surgery. QID dosing will continue until postoperative day 14. Treatment will be tapered from QID to BID during the interval between postoperative days 15 and 21. Treatment will be further tapered from postoperative day 22 until day 28 to QD with the last dose being administered on the day prior to Visit 6 (Postoperative Day 28).

Parents/legal guardians will be trained with regard to the instillation of eye drops prior to administration of the initial dose.

Site personnel will instruct the subject's parent/legal guardian on the proper instillation of their study medication without using the study drug.

Subject's parent/legal guardian will be instructed to return the study drug at Visits 4, 5 and 6 for weighing, and for collection in the original packaging at Visit 6 or early study discontinuation. Both the Investigator and the subjects will be masked to the study drug assignment.

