5.1.3 Visit 3 (Postoperative Day 1; First Calendar Day after Surgery)

At Visit 3, the following assessments will be performed:

NOTE: All ocular assessments and VA will be performed bilaterally.

- AEs and changes in concomitant medications
- the unmasked designee must weigh both bottles of study drug
- ocular symptoms
- pediatric VA
- biomicroscopy
- IOP measurement

NOTE: Measurement of IOP must occur after the assessment of ocular symptoms, VA and biomicroscopy.

NOTE: If, at any time point after surgery, IOP is elevated, treatment or intervention is left to the Investigator's discretion and the subject is to continue the study.

- fundoscopy, if not performed during surgery

NOTE: Topical antibiotic drops should be administered at least 15 minutes AFTER study drug application.

- review and collect study drug administration diary for compliance. Instruct subject's parent/legal guardian to record time of each instillation on the diary and to bring the diary and study drug (both bottles) to their next visit. Remind subjects that no other information should be recorded in the diary
- dispense new diary
- the unmasked designee must redispense study drug
- instruct subject's parent/legal guardian to continue dosing the study drug QID, at approximately four hour intervals for the next 2 weeks

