5.1.5 Visit 5 (Postoperative Day 14, ±3 days)

At Visit 5, the following assessments will be performed:

NOTE: All ocular assessments and VA will be performed bilaterally.

- AEs and changes in concomitant medications
- the unmasked designee must weigh both bottles of study drug
- ocular symptoms
- pediatric VA
- biomicroscopy
- IOP measurement

NOTE: Measurement of IOP must occur after the assessment of ocular symptoms, VA and biomicroscopy

- fundoscopy (it is at the Investigator's discretion whether to perform fundoscopy with or without mydriasis)
- review study drug administration diary for compliance. Instruct subject's parent/legal guardian to record time of each instillation in the diary and to bring the diary and study drug (both bottles) to their next visit. Remind subject's parent/legal guardian that no other information should be recorded in the diary
- dispense diary
- the unmasked designee must re-dispense study drug
- remind subject's parent/legal guardian that the dosing is BID for the rest of the week and QD for the last week

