5.1.6 Visit 6 (Postoperative Day 28, ±7 days; End of Treatment)

At Visit 6, the following assessments will be performed:

NOTE: All ocular assessments and VA will be performed bilaterally.

- AEs and changes in concomitant medications
- the unmasked designee must weigh both bottles of study drug and collect all used and unused study drug (both bottles)
- collect diaries

- ocular symptoms
- pediatric VA
- biomicroscopy
- IOP measurement

NOTE: Measurement of IOP must occur after the assessment of ocular symptoms, VA and biomicroscopy

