9.2.2 Treatment Compliance

Study drug compliance will be calculated for each subject by taking into account whether a subject takes all doses of study drug as instructed. Compliance will be based solely on the subject diaries. The study drug compliance rate will be presented overall, at Visit 4, Visit 5 and Visit 6. The study drug compliance rate for Visit 5 will be calculated by dividing the total number of dosing recorded in the diary for the subject for that period by the total number of days times 4 and then multiplying by 100. The first day of dosing will be ignored entirely, since subjects may be compliant with any number of doses.

The overall study drug compliance rate will be calculated by dividing the total number of dosing recorded in the diary for a subject across the entire treatment period by the total number of days times 4 for days \leq 14, times 2 for days between days 15 and 21 and times 1 for days between 22 and 28 and then multiplying by 100. The first day of dosing will be ignored entirely, since subjects may be compliant with any number of doses. The number and percentage of subjects in each of the following compliance rate categories will also be reported: (\leq 50%, 51-60%, 61-70%, 71-80%, 81-120%, and $>$ 120%). Percentages will be calculated out of the number of subjects who returned diaries from that dosing period. The number and percentage of subjects in each compliance rate category will be presented overall, at Visit 4, Visit 5 and Visit 6.

10 Statistical Analyses

All efficacy analyses will use a 2-sided alpha = 0.05 test unless otherwise stated. No adjustments will be made for multiplicity testing.

Analyses will be performed on the ITT and PP analysis set for both the primary efficacy endpoint and secondary efficacy endpoints. The safety analyses will be performed on the SAF.

All continuous efficacy endpoints will be summarized graphically by treatment group displaying the mean and corresponding standard errors at each time point for the primary efficacy endpoint or line graphs of the continuous secondary efficacy endpoints over scheduled time.

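### Dose changes are set by calendar day in the design sections but by weeks from a visit in the parent instructions; separately, the Visit 5 compliance denominator ignores the taper

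*Protocol*

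**What the plan says.** **Calendar rule.** Protocol 3.1 states "QID dosing will continue until postoperative day 14, including dosing at appropriate time intervals on the day of a visit". Protocol 4.3 adds "Treatment will be tapered from QID to BID during the interval between postoperative days 15 and 21", followed by QD from Day 22 to Day 28. The Synopsis, Protocol 4.10 and SAP 5.1 and 5.9 give the same days.

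**Visit-based instructions to parents.** None names a calendar day.
- Visit 3 (Protocol 5.1.3): QID "at approximately four hour intervals for the next 2 weeks".
- Visit 4 (5.1.4; window Day 7 ±2): "the dosing is QID for another week and then BID for one week".
- Visit 5 (5.1.5; window Day 14 ±3, the primary assessment): "the dosing is BID for the rest of the week and QD for the last week".

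**End of dosing.** Protocol 3.1 and 4.3 run QD to Day 28 but also place the final dose one day before Visit 6. Protocol 5.1.6 allows Visit 6 on Day 28 ±7.

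**Compliance.** SAP 9.2.2 takes the Visit 5 rate as diary doses for the period divided "by the total number of days times 4 and then multiplying by 100". The same section builds the overall rate with multipliers of 4 up to Day 14, 2 for Days 15-21 and 1 for Days 22-28. Rates are tabulated in bands that include 71-80% and 81-120%.

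**The concern.** There are two separate issues.

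1. A family can attend every visit inside its window, do what it was told at Visit 4, and still follow a schedule that the design section does not describe. With an early Visit 4 the departure begins before Day 14, so it can precede the primary assessment. The per-protocol definition turns on deviations likely to affect the primary outcome seriously, and neither document says whether a dose change made as instructed would count.

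2. The Visit 5 compliance rate assumes four doses on every day of its period. If that period runs past Day 14, the formula expects doses that the calendar schedule does not prescribe. Full adherence then scores below 100%, even though the overall rate in the same section allows for the taper.

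**Working it through.** The plan states no figure on this point. Its main design figure, 98% power, reproduces: 0.35 / (0.47 × √(2/60)) = 4.08; 4.08 − 1.96 = 2.12; Φ(2.12) = 0.983. Nothing below alters it. Days are postoperative days, with surgery on Day 0.

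**Issue 1: last QID day under the Visit 4 wording.** Last QID day = Visit 4 day + 7 if the visit day is not counted, or + 6 if it is. The calendar rule prescribes 14 × 4 = 56 doses on Days 1-14. Each of those days given BID instead of QID removes 2 doses.

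| Visit 4 | Last QID day (visit day not counted / counted) | Doses short by Day 14 |
|---|---|---|
| Day 5 | 12 / 11 | 4 / 6 |
| Day 6 | 13 / 12 | 2 / 4 |
| Day 7 | 14 / 13 | 0 / 2 |
| Day 8 | 15 / 14 | 0 / 0 |
| Day 9 | 16 / 15 | 0 / 0 |

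A Day 5 visit therefore costs 4/56 = 7.1% of scheduled doses (6/56 = 10.7% if the visit day counts). At the nominal Day 7 the two rules agree when the visit day is not counted. After Day 9, QID continues to Day 16 (or 15), past the calendar limit.

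For a Visit 5 on Day 14, the number of completed BID days beforehand is 0 under the calendar rule, and 1 (or 2) under the visit wording after a Day 5 Visit 4.

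**End of dosing.** Visit 6 may fall on Days 28 − 7 = 21 to 28 + 7 = 35, so the day before it is Day 20 to Day 34. At the nominal visit it is Day 27, not Day 28. The overall compliance formula has no multiplier after Day 28.

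**Issue 2: Visit 5 rate for a fully adherent child on the calendar schedule.** Rate = scheduled doses / (4 × days) × 100. The SAP does not define the period, so three readings are shown, for visits on Days 9 and 17:
- Day after Visit 4 through Visit 5 (Days 10-17): (5 × 4 + 3 × 2) / (8 × 4) = 26/32 = 81.3%.
- Visit 4 to the day before Visit 5 (Days 9-16): (6 × 4 + 2 × 2) / 32 = 28/32 = 87.5%.
- Day 1 to the day before Visit 5 (Days 1-16): (14 × 4 + 2 × 2) / (16 × 4) = 60/64 = 93.8%.

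These are the lowest values for such a child within the visit windows. With one missed dose the first reading gives 25/32 = 78.1%, against 25/26 = 96.2% of doses actually scheduled, and the child drops to the 71-80% band. The second gives 27/32 = 84.4% and the third 59/64 = 92.2%, with no change of band.

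**Where the two issues meet.** Take a child who follows the Visit 4 wording exactly (visit day not counted), with visits on Days 5 and 17. The first reading gives (7 × 4 + 5 × 2) / (12 × 4) = 38/48 = 79.2%. The second gives (8 × 4 + 4 × 2) / 48 = 40/48 = 83.3%. The third gives (12 × 4 + 4 × 2) / 64 = 56/64 = 87.5%.

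**The case against.** The calendar rule is stated consistently in many places. The visit texts at Visits 4 and 5 are framed as reminders and match it at nominal visit days. Protocol 8.2 has site staff enter dosing dates in the diary in advance, and diaries are reissued at Visits 3, 4 and 5, so families need not rely on a spoken week count. This mitigates the first issue but does not settle it, because that section says nothing about dose frequency.

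The reach before the primary assessment is narrow. Not counting the visit day, only a Visit 4 on Day 5 or 6 shortens QID before Day 14. With a Visit 5 on Day 11 or 12, no completed BID day precedes it. The Visit 5 and Visit 6 wording acts only from the primary visit onward. All of this stands.

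Three stronger readings are tempting, and the documents support none of them.
- **That the comparison of arms is biased.** Both masked arms receive the same instructions, and nothing in the documents shows an effect on the endpoint.
- **That the mixed wording causes the compliance error.** The four-times denominator is wrong for a late Visit 5 even when every family follows the calendar rule.
- **That the table labels children who followed instructions as non-adherent.** Non-adherence is not defined anywhere, and a fully adherent child on the calendar schedule stays in the 81-120% band. The 78.1% figure needs a missed dose and one particular reading of the period. The 79.2% figure needs an extreme pair of visit dates and a similar choice of convention.

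**Conclusion.** Both issues hold, at modest size. The calendar rule and the visit-based instructions disagree within the permitted windows. The Visit 4 wording moves the last QID day to between Day 12 and Day 16, and costs up to 4 of 56 doses by Day 14 (6 if the visit day counts). This assumes the family follows the spoken instruction literally and the diary does not correct it. The two statements on when dosing ends also conflict.

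Separately, the Visit 5 compliance formula understates adherence once its period runs past Day 14. In the worst case, a fully adherent child on the calendar schedule scores 81.3% to 93.8%, depending on the period assumed. A change of band for that child also requires a missed dose.

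Compliance is not in the primary model and is not a stated per-protocol cut-off, so the second issue affects a descriptive table only. Sample size and power are untouched. The priority lies between a minor correction and one that should be made: the effects are small, but these are rules as written that conflict or give a wrong figure, and they are cheap to correct.

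**What to change.** 1. **Dosing text.** Reconcile the Synopsis and Protocol 3.1, 4.3, 4.10 and 5.1.3 to 5.1.6 with SAP 5.1, 5.8.1 and 5.9. One rule, worded identically everywhere, should say on which day each frequency starts and ends, including the final dose, when a visit is early or late. The parent instructions and the diary should carry the same rule. Which schedule is right is for the sponsor to decide; no position is taken here.

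2. **SAP 9.2.2.** Define the first and last day of each visit period. Use as the Visit 5 denominator the doses scheduled on each day of that period under the reconciled rule. Check the Visit 6 and overall rates against the same rule, so that all the rates agree. The current 4/2/1 multipliers are correct only if the sponsor confirms the calendar schedule.

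The cost is a protocol clarification, revised parent wording and one or two SAP sentences. No data collection or sample size changes. If the parent wording can no longer be changed, the SAP correction can still be made before database lock, together with a statement of how dosing that followed a visit instruction is classified for the per-protocol population.

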5.1.5 Visit 5 (Postoperative Day 14, ±3 days)

At Visit 5, the following assessments will be performed:

NOTE: All ocular assessments and VA will be performed bilaterally.

- AEs and changes in concomitant medications
- the unmasked designee must weigh both bottles of study drug
- ocular symptoms
- pediatric VA
- biomicroscopy
- IOP measurement

NOTE: Measurement of IOP must occur after the assessment of ocular symptoms, VA and biomicroscopy

- fundoscopy (it is at the Investigator's discretion whether to perform fundoscopy with or without mydriasis)
- review study drug administration diary for compliance. Instruct subject's parent/legal guardian to record time of each instillation in the diary and to bring the diary and study drug (both bottles) to their next visit. Remind subject's parent/legal guardian that no other information should be recorded in the diary
- dispense diary
- the unmasked designee must re-dispense study drug
- remind subject's parent/legal guardian that the dosing is BID for the rest of the week and QD for the last week

5.1.6 Visit 6 (Postoperative Day 28, ±7 days; End of Treatment)

At Visit 6, the following assessments will be performed:

NOTE: All ocular assessments and VA will be performed bilaterally.

- AEs and changes in concomitant medications
- the unmasked designee must weigh both bottles of study drug and collect all used and unused study drug (both bottles)
- collect diaries

- ocular symptoms
- pediatric VA
- biomicroscopy
- IOP measurement

NOTE: Measurement of IOP must occur after the assessment of ocular symptoms, VA and biomicroscopy

5.1.7 Visit 7 (Postoperative Day 42, ± 7 days)

At Visit 7, the following assessments will be performed:

NOTE: All ocular assessments and VA will be performed bilaterally.

- AEs and changes in concomitant medications
- ocular symptoms
- pediatric VA
- biomicroscopy
- IOP measurement

NOTE: Measurement of IOP must occur after the assessment of ocular symptoms, VA and biomicroscopy

5.1.8 Visit 8 (Postoperative Day 90, ± 14 days; Study Exit)

At Visit 8, the following assessments will be performed:

NOTE: All ocular assessments and VA will be performed bilaterally.

- AEs and changes in concomitant medications
- ocular symptoms
- pediatric VA
- biomicroscopy
- IOP measurement

NOTE: Measurement of IOP must occur after the assessment of ocular symptoms, VA and biomicroscopy

- fundoscopy (it is at the Investigator's discretion whether to perform fundoscopy with or without mydriasis)
- subject exits from study

5.1.9 Unscheduled Visits

Additional visits may be scheduled, as necessary, to ensure the safety and well-being of subjects. All additional exams should be fully documented in the source documents and on Unscheduled Visit eCRFs, as appropriate. Visits intended to fulfill scheduled visit requirements that fall outside the designated scheduled visit range, are not Unscheduled Visits. In these cases, the visit data will be collected and transcribed to the appropriate scheduled visit eCRF.

If a subject is seen for multiple visits during a given visit timeframe, the data from the visit that is intended to meet the protocol requirements for the scheduled visit should be captured on the visit eCRF. Where such a determination cannot be made, the first visit within the scheduled visit interval will be used for completion of the protocol required scheduled visit eCRF. Data from any additional visits within a scheduled visit interval will be captured on an Unscheduled Visit eCRF.

5.1.10 Missed Visits

If a subject misses any scheduled follow-up visit and cannot be seen prior to the start of the visit range for the next scheduled follow-up visit, the visit is considered missed.

5.2 Post-study Follow-up

If a subject requires further follow-up of AEs upon discontinuation or completion of the study, the Investigator must schedule post-study follow-up visits, as necessary. Refer to Sections 6.3 and 6.4 for follow-up of AEs following study exit.

5.3 Study Completion

Depending on local regulations, Bausch + Lomb Global Clinical Operations will notify the Investigator when to contact the IRB/EC to inform them that the study is complete or Bausch + Lomb will do this on the behalf of the Investigator. In the EU, Bausch + Lomb will inform the regulatory agencies in the concerned member states in addition.

5.3.1 Early Study Termination

If during the study it becomes evident to the Sponsor that the study should be stopped prematurely or placed on hold, appropriate notification will be given to the Investigator(s), IRB/EC, FDA, and appropriate EU regulatory agencies, as applicable. Bausch + Lomb Global Clinical Operations will instruct the Investigators to stop/restart dispensing study materials and will arrange for study closeout, if applicable, at each site.

5.4 Concomitant Medications/Therapy

Administration of all medications used by the subject, the breastfeeding mother, or wet nurse up to 30 days prior to study entry (date ICF signed) through study exit must be recorded in the source documentation and in the Concomitant Medications eCRF. Indications for these medications should be recorded in the subject's Medical History eCRF, as applicable.

5.4.1 Permitted Therapy

Permitted therapy applies to the subject, breastfeeding mother, or wet nurse. Use of topical antibiotics is allowed if they are not used in combination with any steroid in the study eye (eg, Zylet® or TobraDex should not be used). Topical antibiotics used preoperatively and postoperatively are allowed bilaterally and must be recorded in the Concomitant Medications eCRF provided by the Sponsor. Intraoperative use of topical antibiotics or other standard of care surgical medications should be recorded in the source documentation only.

In the event that the subject requires surgery on the contralateral eye at any time during the study, the fellow eye will be treated at the Investigator's discretion with standard of care medication. The standard of care medication must be recorded under concomitant medications in the eCRF provided by the sponsor.

With the exception of the disallowed medications in Section 5.4.2, any medications that, in the Investigator's judgment, will not interfere with the study parameters are allowed to be used concurrently by the subject, breastfeeding mother, or wet nurse; for example, the following medications are permitted:

- systemic analgesics (eg, acetaminophen/paracetamol)
- oral birth control pills
- ≤100 mg/day acetylsalicylic acid (for breastfeeding mother/wet nurse only)
- hypoglycemic agents
- anticholesterol medications
- insulin
- systemic antimicrobials
- antidepressants
- thyroid preparations
- antihypertensive agents
- cardiovascular agents

- Standard anesthetic and mydriatic agents may be used intraoperatively or for postoperative diagnostic purposes (ie, IOP and funduscopy). Ocular NSAIDs may not be used for mydriasis or at any other time point during the study in the study eye. Ocular therapy with NSAIDs and/or corticosteroids in the fellow eye is permitted.
- The long term use of systemic NSAIDs is not allowed during the study. If unavoidable, use of systemic NSAIDs can be permitted only after Visit 5, but should be kept to a minimum and treatment duration with NSAIDs should be kept short (for example, one day per treatment period).
- Topical ocular hypotensive agents, if used at the end of surgery by the study site, will be used with ALL subjects treated at that site.
- Intracameral injection of antibiotic is allowed at the end of surgery.

